We propose a 5-year study to test the effectiveness of a culturally appropriate, theory-based intervention to increase MVPA among Latinas in the LRGV. This study is a continuation of our ENLACE pilot study. We will involve 8 CRCs affiliated with the Colonias Program in the study. The CRCs will be randomized to one of two conditions: (a) ENLACE PA intervention (n=4 CRCs), or (b) attention control (n=4 CRCs). By randomizing at the CRC-level the intervention can be implemented by the promotora to all study participants, thus reducing the risk of contamination that would be present with promotora- or participant-level randomization. This approach also allows us to implement an ecological intervention, where each CRC can implement and promote PA activities and display materials to support the intervention messages. A total of 864 Latinas ages 18-64 years will be recruited from within the service area for these 8 CRCs. The study will be conducted in 3 cohorts of 288 women (36 per CRC in each cohort). Participants will be assessed at baseline, 16 weeks (immediate post intervention), and 40 weeks (delayed post intervention). The primary outcome is minutes per week of MVPA. Secondary outcomes are physical fitness and weight maintenance. Consistent with our approach, we will establish a community advisory group and engage promotoras in conducting participatory community assessments. Finally, we will recruit sub-sample of 4 intervention participants from each CRC cohort to complete two in-depth interviews, immediately following the PA intervention (16 weeks) and after the maintenance intervention period (40 weeks), to evaluate the impact of Latinas’ social and community environment context on their success (or failure) in increasing MVPA and maintaining the behavior change.

Study Design

```

graph TD
    A[8 promotoras] --> B[8 groups of 8-10 women per group (n=68)]
    A --> C[Baseline Assessment N=864]
    C --> D[Randomize]
    D --> E[Physical Activity Intervention (n=432)]
    D --> F[Attention Control (n=432)]
    E --> G[16-week Assessment]
    G --> H[In-Depth Interviews (n=48)]
    H --> I[40-week Assessment]
    I --> J[In-Depth Interviews (n=48)]
    F --> K[16-week Assessment]
    K --> L[40-week Assessment]
    
```

FORM C

IRB #	HSC20110460H
--------------	---------------------

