D.4.2.4. Environmental Change. Social ecological models^{33, 34, 78} emphasize that the environment is an important influence on health behavior. We will work with *promotoras* at the four ENLACE PA intervention CRCs to create a site atmosphere that promotes PA. Examples might include educational posters, promotional activities to increase awareness and appeal of existing resources, notices of related community events, and a display board highlighting the ENLACE Program and participants who have been successful in the program. *Promotoras* will also increase the number of PA program offerings at the CRC by identifying and training volunteer walk leaders and using an exercise DVD library to offer regularly scheduled group exercise classes.

D.4.2.5. Attention Control Intervention. Attention control participants will receive a research-tested first aid and home safety program developed for Hispanic migrant adolescents and their families⁷⁹. We selected the home safety/first aid as the attention control condition because changes in these behaviors should have no impact on PA, the curriculum is available in Spanish, and has been shown to improve first aid knowledge and emergency response skills. In addition, the *Colonias* Program staff indicated it was relevant topic for families in the *colonias*. The program includes 8 sessions that last 1.5-2 hours. These sessions will be offered twice per month to extend them over a 16 week period. The session content ranges from identifying household safety hazards to disaster preparedness. During the 24 week maintenance phase, *promotoras* will contact participants by phone each month and conduct monthly home visits to distribute health education materials on first aid and home safety from CDC, state health department and other reliable health organizations (e.g., Red Cross). Attention control participants will not receive telephone counseling calls.

Measurement and Evaluation

Standardized data collection protocols will be carried out for all participants at baseline, 16-, and 40-weeks.

Primary Outcome Measures:

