Physical Fitness. The YMCA 3 minute step test will be used to assess changes in cardiorespiratory fitness associated with increased PA⁸⁶. We will also apply the equations developed by Juraca et al.,⁸⁷ should we find that women cannot perform the standard fitness assessment.^{86, 87}

Anthropometrics. **Weight** (to the nearest 0.1 kg) and **% body fat**, will be measured using a portable Tanita Body Composition Analyzer SC-331S. **Height** (measured to the nearest 0.1 cm) will be obtained using a stadiometer at baseline only. Participants will be asked to remove their shoes prior to both measurements. **BMI** will be calculated as weight (kg)/height squared (m^2). **Waist circumference** will be measured at the midway between the iliac crests and the lower ribs, whereas hip circumference will be measured at the level of the greatest protrusion of the buttocks when the subject is standing erect with feet together. All will be measured twice and the average used. We will use the definition of **weight maintenance** proposed by Stevens et al.,⁸⁸ indicating that a change in body measurement (BMI or % body fat) $< \pm 3\%$ is consistent with weight maintenance in adults.

Mediator Variables:

Self Efficacy. Sallis et al.'s⁸⁹ self-efficacy scales for exercise behaviors (12 items) have been widely used and have strong psychometric properties, with test-retest reliability ranging from 0.43 to 0.68, internal consistency ranging from 0.83 to 0.93, and demonstrated criterion-related validity⁸⁹.

Social Support. The social support for PA (13 items) is based on Sallis et al.'s⁹⁰ scale, where participants rate the extent to which family and friends are supportive of PA changes. These measures have shown acceptable test-retest reliability ($r = 0.55$ to 0.86), internal consistency ($\alpha = 0.61$ to 0.91), and concurrent criterion-related validity⁹⁰.

Benefits and Barriers. Marcus et al.'s Decisional Balance Scale for PA⁹¹ assesses perceived benefits (pros) and perceived barriers (cons) of PA.

Collective Efficacy. Sampson et al.'s⁹² measure of collective efficacy is composed of two related subscales on mutual trust/cohesion and shared expectations for social control.

Center for Epidemiological Studies Depression Scale (CES-D) assesses depressive symptoms and has acceptable internal consistencies of .87 and above^{93, 94}.

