Mediation Analyses (Aim 2c). As outlined by MacKinnon^{103, 104}, mediation will be assessed by conducting two regression models. The first model will regress change in the hypothesized mediator (e.g., social support, self-efficacy) on intervention group (intervention vs. control) (α coefficient path). The second model will regress change in the outcome variable (e.g., MVPA) on intervention group and change in the hypothesized mediator (β coefficient path). To assess the magnitude of the effect for each potential mediator, the Sobel-Goodman test will be conducted using *sgmediation* in STATA 11 SE¹⁰⁵. This method provides direct and indirect effect estimates, proportion of effect explained by mediator, and significance testing.

Attrition Analyses. We will compare all baseline demographic, cognitive, and behavioral variables of participants lost to follow-up with baseline data of the cohort, to determine possible selective or differential (by treatment condition) attrition. For instance, analyses will be conducted to determine if participants with greater weight or lower PA disproportionately drop out of the study. Selective attrition (i.e., do dropouts differ from the cohort as a whole?) will be considered a threat to external validity or generalization. Presence of differential attrition (i.e., difference in dropouts between treatment conditions) will be considered a threat to internal validity. To the extent that some subjects are lost to follow-up, analysis for the primary and secondary hypotheses will be carried out under the intent-to-treat principle.

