Qualitative Data Analysis Plan. Audio recordings of interviews will be transcribed verbatim in the source language and returned to the PI in paper and electronic (Microsoft Word) formats. A data collection assistant will review the paper transcripts for quality control purposes to make sure that the paper and electronic transcripts are as accurate and reflective of the interview as possible. All identifying information will be removed from transcripts. The transcript files will be imported into AtlasTi software for qualitative data management and analysis. All data in paper format will be stored in locked cabinets in locked offices. [name] will lead the qualitative analysis of the interview data in the source language, using thematic analysis procedures and the constant comparison method^{97,106}. For presentation and dissemination, selected excerpts of the Spanish-language qualitative data will be translated into English.

Power and Sample Size: Power calculations were conducted to determine the minimum detectable effect size based on a desired power achievement =0.80 using Optimal Design¹⁰¹. Setting the standard effect size to 0.50 and an expected intraclass correlation of .01, we have calculated a minimum number of 83 subjects per site will be needed. Based on a 76% retention rate from the pilot study, we will sample an additional 25 subjects to maintain statistical power throughout study duration for a total of 108 per site and an overall total of 864 subjects.

In-Depth Interviews: With a resulting sample of 96 interviews, we anticipate meeting the requisites of saturation and sufficiency⁹⁶. Saturation refers to the point in the study at which analysis of the interview data results in no new properties or dimensions⁹⁷. The greater the amount of pertinent (on-topic) data obtained from participants, the smaller number of participants required for saturation; thus, well-devised and conducted interviews with skilled probing reduces the need for large sample sizes in order to fully assess the phenomena under study⁹⁸. Sufficiency is the extent to which the participant sample encompasses the range of variability in the participant characteristics, especially those of known relevance to the topic⁹⁹. Due to the relative homogeneity of our participants, a sample of 96 interviews is expected to be sufficient.

6.b. List of the study intervention(s) being tested or evaluated under this protocol

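### The first mediation model (Aim 2c) regresses raw mediator change on arm and omits the baseline mediator score, losing up to about 14 points of a-path power for self-efficacy and 10 for social support at an assumed 0.3 SD effect

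*Protocol*

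**What the plan says.** Section 6.a, Mediation Analyses (Aim 2c), sets out two regressions and a test.

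- First model (a-path): "The first model will regress change in the hypothesized mediator (e.g., social support, self-efficacy) on intervention group (intervention vs. control"). No covariate is named.
- Second model (b-path): "The second model will regress change in the outcome variable (e.g., MVPA) on intervention group and change in the hypothesized mediator".
- Test: "the Sobel-Goodman test will be conducted using *sgmediation* in STATA 11 SE". The paragraph expects direct and indirect effects and the proportion explained by the mediator.

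Baseline mediator scores exist. Under Measurement and Evaluation: "Standardized data collection protocols will be carried out for all participants at baseline, 16-, and 40-weeks". The table in section 6.d also lists the mediator questionnaires three times.

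Mediator Variables gives reliability for two of the four mediators named in Aim 2c. For self-efficacy: "with test-retest reliability ranging from 0.43 to 0.68, internal consistency ranging from 0.83 to 0.93". For social support: "These measures have shown acceptable test-retest reliability ($r = 0.55$ to 0.86"). Decisional balance and collective efficacy have no figure.

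**The concern.** With arm as the only regressor and change as the outcome, the model assumes that each point of baseline score carries over fully to follow-up. If the true slope is below 1, the subtraction adds baseline noise to the arm contrast. The arms are also few: "a) ENLACE PA intervention (n=4 CRCs), or (b) attention control (n=4 CRCs"). A chance baseline difference is therefore plausible, and regression to the mean then moves the estimated mediator change.

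The a-path is the randomised half of every indirect effect in Aim 2c. Extra noise there widens the interval for each mediator and makes a real one easier to miss, although the value that would remove the noise has already been collected.

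**Working it through.** **The plan's own figure.** Under Power and Sample Size: "we have calculated a minimum number of 83 subjects per site will be needed", for effect 0.50, ICC .01 and power 0.80. No alpha is given. The noncentrality is sqrt(J d² / (4[ICC + (1 − ICC)/n])) with J − 2 = 6 df. With J = 8, d = 0.50 and n = 83, the bracket is 0.01 + 0.99/83 = 0.02193, so the noncentrality is sqrt(2/0.08771) = 4.78. Power is 80.1% at two-sided 0.01, and n = 82 gives 79.9%. At two-sided 0.05 only 30 per site are needed. The figure is thus reproduced, but only at an inferred alpha of 0.01.

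**Inputs for this point.** From the protocol: 8 centers, 83 evaluable per site (664 women), ICC .01, and the reliabilities above. Assumed, because the protocol does not state them: two-sided 0.05, a mediator effect of 0.3 SD, reliability standing in for the baseline-to-16-week correlation rho, and the same rho at center and individual level.

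**Variance.** For a mediator with unit variance:

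- change score: 2(1 − rho)
- baseline-adjusted: 1 − rho²
- ratio: (1 + rho)/2

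**A-path power.** SE = sqrt(V × [1 + 82 × 0.01] × 4/664) = sqrt(V × 0.01096). At rho 0.43 the change-score SE is sqrt(1.14 × 0.01096) = 0.112 and the adjusted SE is sqrt(0.8151 × 0.01096) = 0.095. Power comes from the noncentral t with 6 df:

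| rho | ratio | power, change only | power, baseline added | gain (points) |
|---|---|---|---|---|
| 0.43 (self-efficacy, low) | 0.715 | 61.2% | 75.3% | 14.1 |
| 0.68 (self-efficacy, high) | 0.84 | 84.5% | 89.9% | 5.4 |
| 0.55 (social support, low) | 0.775 | 71.2% | 81.4% | 10.2 |
| 0.86 (social support, high) | 0.93 | 99.3% | 99.6% | 0.2 |

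**Sensitivity of the a-path gain.**

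- Effect 0.2 SD: 33% to 43%, 40% to 48% and 52% to 59% at rho 0.43, 0.55 and 0.68.
- Effect 0.5 SD: about 3 points or less, since power is already about 96% or more.
- Alpha 0.01, effect 0.3 SD: 8.8 to 12.5 points for self-efficacy and 2.1 to 11.1 for social support. At 0.01 the 0.5 SD case is no longer negligible (74.0% to 88.3% at rho 0.43).
- Center-level correlation, self-efficacy: 3.3 to 6.9 points if it is 0.8, 0.2 to 1.5 if it is 1.0, and 11.5 to 18.2 if it is 0.
- No cluster term, as literally written, self-efficacy: nominal power changes by 0.2 to 3.8 points (95.2% to 99.0% at rho 0.43).

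**The mediation test itself.** The Sobel statistic is ab / sqrt(a² s_b² + b² s_a²), so only one of the two variance terms shrinks. Simulation with 664 women, no clustering and assumed b = 0.15, adjusting the first model only, gave:

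| rho | 0.2 SD | 0.3 SD |
|---|---|---|
| 0.43 | 53% to 68% | 87% to 94% |
| 0.55 | 57% to 69% | 86% to 91% |
| 0.68 | 60% to 66% | 81% to 83% |

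Over repeated simulations at the self-efficacy correlations, the gain lies at about 6 to 17 points for 0.2 SD and about 2 to 9 for 0.3 SD.

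**Chance imbalance.** The SD of the baseline arm difference is sqrt(0.01096) = 0.105 SD. Raw change carries (1 − rho) of it: at rho 0.43, 0.57 × 0.105 = 0.06 SD, with a 95% range of about ±0.12 SD. Against a 0.3 SD effect that is 20% and 40%. This is not a further loss on top of the power figures: 2(1 − rho) − (1 − rho²) = (1 − rho)², so the extra variance is exactly this carried imbalance.

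**The case against.** **The size is easily overstated.** A reader might take 5 to 14 points as the loss of power for Aim 2c. The documents do not support that. It is a-path power, for one of four mediators, in a clustered 6-df test, whereas the mediation paragraph names no cluster term. The mediation test loses less at the same 0.3 SD, and two mediators have no stated reliability. This objection stands in full, and the claim is limited accordingly.

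**Raw change is not wrong.** A reader might also infer that the a-path estimate is biased. With arm randomised, it is unbiased over randomisations. What is lost is precision, or, in the one allocation realised, protection against the imbalance that happened to occur.

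**The fix has a price.** Total = direct + indirect is exact in least squares only when both models carry the same covariates. With the first model alone adjusted, simulation shows a gap with SD about 0.002 to 0.007, against an indirect effect of 0.15 × 0.3 = 0.045. Putting the baseline mediator in both models restores the identity, but it costs b-path precision. Indirect-effect power at 0.3 SD then goes from 87% to 86%, 86% to 83% and 81% to 76% (rho 0.43, 0.55 and 0.68), and the gain at 0.2 SD is at most 5 points. This stands as a cost. It does not defeat the point, because the estimator with only the first model adjusted stayed unbiased and was more precise in the scenarios run.

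**Covariates may be left to an SAP.** Often so, but here the protocol writes out the regressors of both models, so the text as it stands fixes a specification.

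**Conclusion.** The point holds as an avoidable loss of precision in a stated model for a secondary aim. Under the listed assumptions it costs about 5 to 14 points of a-path power for self-efficacy and about 0 to 10 for social support at 0.3 SD. For the Sobel test with b = 0.15 and self-efficacy correlations, it costs about 2 to 9 points at 0.3 SD and 6 to 17 at 0.2 SD.

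The least certain inputs are the 16-week correlation and its center-level counterpart. An individual correlation below the reliability figures would enlarge the loss; very stable center means would nearly remove it. The figures do not show that Aim 2c as a whole is underpowered, since the protocol gives neither a mediator effect nor an alpha.

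**What to change.** In section 6.a, Mediation Analyses (Aim 2c), restate the first model as the 16-week mediator, or its change, regressed on intervention group and the baseline value of that mediator. The arm coefficient is the same either way. Use that coefficient and its standard error in the indirect effect, and leave the second model as it is.

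Add two statements. First, the indirect effect and its standard error are computed from the two regressions, not taken from a single sgmediation run, because the covariates differ. Second, total = direct + indirect then holds approximately, so the proportion mediated is reported as approximate. If an exact decomposition matters more than power, the baseline mediator can go in both models, giving up most or all of the gain.

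The cost is a few sentences and one covariate per mediator model, with no new data, visits or participants.

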The long-term goal of the ENLACE is to reduce obesity and obesity-related morbidity and mortality by increasing the number of Latinas who meet national PA guidelines for adults9. We hypothesize that Latinas at the PA intervention sites will significantly increase their MVPA levels as a result of addressing their specific individual and environmental barriers and enhancing their social support and collective efficacy, compared to Latinas at the attention-control sites.

Primary aim: Test the effect of a 16-week, promotora-led PA intervention on minutes per week of MVPA (primary outcome) among Latinas in South Texas, compared to an attention-control group.

Secondary aims: a) Test the effect of the 16-week promotora-led PA intervention on physical fitness and weight maintenance (secondary outcomes); b) assess the maintenance of primary and secondary outcomes 6 months after the end of the intervention; c) examine the role of self-efficacy for PA, social support, decisional balance, and collective efficacy as mediators of changes in MVPA; and d) evaluate the impact of Latinas' social and community environment context on their success (or failure) in increasing MVPA and maintaining the behavior change.

Eight community resource centers (CRCs) in four Lower Rio Grande Valley (LRGV) counties—Starr, Hidalgo, Willacy and Cameron—will be randomly assigned to either the ENLACE PA Intervention (4 CRCs) or the attention-control condition (4 CRCs). We will recruit 864 Latinas ages 18 - 64 who do not meet national PA guidelines from colonias (unincorporated settlements where many people live in impoverished conditions and lack basic services) in the service area of the eight CRCs. Participants from CRCs randomized to the ENLACE PA Intervention (N = 432; 108 women per CRC) will receive the 16-weekly promotora-led group sessions, followed by 24 weeks of a maintenance intervention (monthly promotora-delivered newsletter and bi-monthly telephone counseling). The goal for the 16 weeks will be for women to engage in 30 minutes per day of MVPA on 5 or more days per week. The attention-control group (N = 432; 108 women per CRC) will receive 8 promotora-led group sessions twice a month on home safety/first aid and monthly generic health education materials during the maintenance intervention period. Standardized measurement of primary and secondary outcomes will occur at baseline, immediate (16 weeks) and delayed (40 weeks) post-intervention.

2. Background.

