Perceived Stress Scale (PSS-10) examines the degree to which specific situations are deemed as stressful in the past week. The PSS is well validated and has been used in many studies examining the association between stress and health⁹⁵.

Perceptions of Environmental Supports. The 10 items were adapted from the International Physical Activity Prevalence Study (IPS) Self-Administered Environmental Module to assess environmental supports and capture participants' sense of community opportunities for PA.

Food Frequency Questionnaire (FFQ) is approximately a 110 food item questionnaire designed to estimate usual and customary intake of a wide array of nutrients and food groups that is to be conducted by interviewer-administration.

Demographic Variables:

Demographic data (collected at baseline only) will be used to describe the study participants and facilitate statistical analyses where potential confounding by these variables should be controlled. Information will include age, current marital status, educational attainment, acculturation, nativity, current employment status and occupation, household size, family income.

In-Depth Interviews:

Individual in-depth interviews will be conducted with a subset of participants in the PA intervention. The purpose of the interview is to explore participants' personal experiences of behavior change and identified barriers and enablers to success/failure, including intrapersonal, social and environmental influences (Aim 2d). These qualitative data will complement and explicate quantitative findings from the intervention (Aim 2c). All participants in the PA intervention that complete the 16 week immediate post intervention assessment will be in the population to be sampled for the qualitative interviews. After each cohort completes the 16 week assessment, 4 participants per CRC, stratified by success or failure (based on level of improvement in MVPA), will be randomly selected to take part in a two-part series of individual, in-depth interviews (N=64). Participants will be classified as successful if they show a minimum increase of 15 minutes/day MVPA (objectively measured). Each participant selected will be interviewed twice, immediately after the 16 week and 40 week assessments.

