Primary Outcomes (Aim 1 & Aim 2b). MVPA outcomes will be self-reported behavior of a typical week measured with the CHAMPS instrument (minutes/week MVPA) and objective measurement from the accelerometer (minutes/day MVPA). Averages for each MVPA outcome at each time-point will be calculated and compared for the intervention versus the attention-control group and ANOVA tests will be performed to evaluate for significant differences between groups. Assessment will be made to determine direction- e.g. increases or decreases- of change between baseline and post-intervention, and baseline and 6-month follow-up. Using STATA 11 to conduct our modeling we will use a regression that is both multilevel and temporal in nature. Mixed-effects regression can be conducted using the `xreg`, `xtgee` and `xtlogit` command in STATA 11 SE¹⁰², depending on the structure of the outcome variable. In this case, time-points of measurement are nested within subjects in a random intercept model. Random coefficient modeling will be conducted using random effects variables at level 2 (subject level) that will be both fixed (nativity, occupation, education, baseline age, etc.) and time varying (perceptions over time, behavior over time, income). Below we represent the equation for a binomial outcome model

$$\log(\mu_{ij}) = x'_{ij} \beta_1 + x'_{ij} \beta_2 \quad (i = \text{level 1-repeated MVPA measures over time}, j = \text{level 2- Individual level covariates})$$

Whereas β_{ij} represents the expected change in the log of the mean unit change of x_{ij} A one unit change in x_{ij} corresponds to an increase β_{ij} in the log of the average.

Secondary Outcomes (Aim 2a). Similar methodology will be implemented in this analysis as in AIM 1. Our outcome variables

FORM C

IRB #	HSC20110460H
-------	--------------

for aspect of the study will be physical fitness, BMI and anthropometric measures of body fat. Averages for physical fitness, BMI and body fat will be calculated for intervention versus the attention-control group and ANOVA tests will be conducted to evaluate significant cross-sectional differences between the intervention and attention-control groups. Evaluation of temporal changes between each time-point will be made. Mixed effect regression models will be conducted as described in Aim 1.

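### The Aim 2c mediator-to-MVPA model names only arm and mediator change, so a baseline factor that drives both changes biases the indirect effect, in either direction

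*Protocol*

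**What the plan says.** Secondary aim (c), in section 1 of the protocol, is to "examine the role of self-efficacy for PA, social support, decisional balance, and collective efficacy as mediators of changes in MVPA". Section 6.a, under Mediation Analyses (Aim 2c), gives two regressions for this:

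- Arm to mediator: "The first model will regress change in the hypothesized mediator (e.g., social support, self-efficacy) on intervention group".
- Mediator to outcome: "The second model will regress change in the outcome variable (e.g., MVPA) on intervention group and change in the hypothesized mediator".

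Then "the Sobel-Goodman test will be conducted using *sgmediation* in STATA 11 SE", and the protocol adds: "This method provides direct and indirect effect estimates, proportion of effect explained by mediator, and significance testing". Neither regression lists a covariate or a baseline score. No assumption about confounding of the mediator and no sensitivity analysis is stated.

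On what is randomised, section 3 says: "The CRCs will be randomized to one of two conditions".

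Two other places in section 6.a bear on adjustment. Demographic Variables says that these data will "facilitate statistical analyses where potential confounding by these variables should be controlled". Primary Outcomes (Aim 1 & Aim 2b) lists covariates for the mixed model, "fixed (nativity, occupation, education, baseline age, etc.) and time varying (perceptions over time, behavior over time, income"; Secondary Outcomes (Aim 2a) takes over that model. The Aim 2c paragraph refers to neither.

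**The concern.** Randomisation protects the arm-to-mediator path. It does not protect the mediator-to-MVPA path, which compares women within an arm whose self-efficacy or support happened to change by different amounts. Age, employment, household size or depressive symptoms at baseline could plausibly influence both how much a woman's self-efficacy changes and how much her activity changes. The two-regressor model credits that shared influence to the mediator.

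The indirect effect is the product of the two paths, so a distorted second path distorts the product, the proportion explained and the test. Aim 2c exists to say which mechanism carried the intervention, and programme designers would use the answer to decide which components to keep. The protocol names covariates for the arm comparison, which randomisation already protects, and none for the path that it does not protect.

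**Working it through.** The protocol gives no figure for the mediation analysis, so there is none to reproduce. The check is algebra, then a hand calculation, then simulation.

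**Inputs.** Sample size: 83 women per site (Power and Sample Size) × 8 sites = 664. Test: Sobel, two-sided 5%. Assumed, because the protocol gives no value: arm effect on mediator change a = 0.5 SD; true mediator effect b = 0; share of each change explained by the baseline variable, 2%, 5% or 10%. Clustering by centre is left out.

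**Bias.** Let a baseline variable X (SD 1) shift mediator change by g and MVPA change by h, with each change scaled to unit within-arm variance. Without X, the mediator slope converges to b + gh and the indirect effect to a(b + gh). A larger sample does not remove gh. If X explains the same share R² of both changes, in the same direction, then g = h = √R² and gh = R²: 0.02, 0.05 or 0.10.

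**Hand calculation.**
- SE of a ≈ 2/√664 = 0.0776, so z_a = 0.5/0.0776 = 6.44.
- SE of the mediator slope ≈ 1/√664 = 0.0388, so z_b has mean gh/0.0388.
- Sobel z = z_a·z_b/√(z_a² + z_b²). It passes 1.96 when |z_b| > 1.96/√(1 − (1.96/6.44)²) = 1.96/0.953 = 2.06.
- Without confounding: 2 × P(Z > 2.06) = 4%.

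| Share of both changes | gh | mean z_b | Rate by hand | Simulated, as written | Simulated, X in both models |
|---|---|---|---|---|---|
| 2% | 0.02 | 0.52 | 7% | 6–7% | about 4% |
| 5% | 0.05 | 1.29 | 22% | 21–22% | about 4% |
| 10% | 0.10 | 2.58 | 70% | 68–71% | about 4% |

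**Spurious proportion explained.** With an assumed direct effect of 0.5 SD, it is a·gh/(a·gh + 0.5): 0.010/0.510 = 2%, 0.025/0.525 = 5%, 0.050/0.550 = 9%. The false indirect effect is modest in size even where it is often significant.

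**Dependence on the arm effect on the mediator.** With a = 0.3 SD, g = h = 0.2 (4% of both changes) gives 9% false mediation, and g = h = 0.3 (9%) gives 45%. With a = 0 the rate stayed at or below 5% in every case tried.

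**Opposite direction.** With true b = 0.3, g = 0.4 and h = −0.4, the slope converges to 0.3 − 0.16 = 0.14. With a = 0.5 the indirect effect falls from 0.15 to 0.07.

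**Change scores against adjustment for baseline scores.** Adding baseline mediator and baseline MVPA to the change-score model gives the same mediator slope as regressing 16-week MVPA on the 16-week mediator and both baselines. Two structures were tried, with mediator retest correlation 0.55 (inside the 0.43 to 0.68 that the protocol gives for self-efficacy), MVPA retest 0.5 (assumed) and b = 0. The mediator–MVPA correlation is the baseline one.

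| Structure | Correlation | As written | With both baseline scores |
|---|---|---|---|
| Stable trait shared at both visits | 0.14 | 4% | 12–21% |
| Stable trait shared at both visits | 0.3 | 4% | 64–76% |
| Each score regresses from its own baseline | 0.14 | 12% | 3–5% |
| Each score regresses from its own baseline | 0.3 | 38–43% | 3–4% |

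Ranges cover the simulation set-ups tried. The ranking reverses between the structures, and the protocol does not say which applies.

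**The case against.** The best defence has four parts.

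- **Change scores are already a safeguard.** They cancel any trait, measured or not, that shifts the level of mediator and MVPA equally at both visits. The stable-trait rows above show this. It stands, and it limits the concern to factors related to change.
- **The protocol intends to control demographic confounding, and a covariate list can wait for the SAP.** This stands in part. The Aim 2c paragraph does not rule out adjustment. But it does write out the regressors of both models, and the general remark on demographics is not tied to them. An analyst following the paragraph would fit unadjusted models.
- **The confounding strengths are hypothetical.** This stands. At 2% of both changes the false-positive rate is close to nominal.
- **It is one secondary aim.** This stands.

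A reader might go further in three ways that the documents do not support. One is that mutual regression to the mean alone makes false mediation near certain. Very high rates at small baseline correlations arise only if mediator and MVPA are correlated at baseline and not at all at 16 weeks, and nothing in the protocol suggests that pattern. Another is that the change-score model should be replaced by 16-week scores adjusted for baseline. That only exchanges one untestable assumption for another. The third is that confounding always appears as mediation. It can equally hide it, and a false positive needs an arm effect on the mediator.

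**Conclusion.** The concern holds in limited form. As written, the mediator-to-MVPA model leaves a non-randomised path unadjusted, and a baseline factor that drives both changes biases the slope and the indirect effect. At the assumed 0.5 SD arm effect on the mediator and no true mediator effect, false mediation runs from about 7% to about 70% as the factor's share of both changes goes from 2% to 10%; adjustment brings it to about 4%. These figures show sensitivity. They do not predict the rate in this trial, because the protocol gives neither the arm effect on any mediator nor the strength of any confounder, and centre clustering was left out. The primary comparison is not touched. The change should be made because it is cheap and Aim 2c is a named aim, but the trial's main conclusion does not depend on it.

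**What to change.** In section 6.a, Mediation Analyses (Aim 2c):

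1. Keep both change-score models and add to each the same fixed set of baseline covariates: age, education, employment, household size and baseline CES-D. All are already collected.
2. Add a sensitivity analysis that also includes baseline mediator and baseline MVPA. Report both forms and whether they agree, because they rest on different assumptions that the data cannot test.
3. State that the indirect effect and the proportion explained are non-randomised evidence, and that confounding by unmeasured or post-baseline factors may remain.

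The cost is some rewording, a few degrees of freedom and one additional analysis. No visit or measurement is added. Adjustment reduces confounding only as far as the listed covariates capture it.
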